# 5.4 Study Drug Treatment

The duration of blinded study drug administration will be 7 days.

Subjects randomized to lefamulin will receive oral lefamulin 600 mg q12h for 5 days (10 doses) and oral moxifloxacin placebo q24h for 7 days (7 doses). Subjects randomized to moxifloxacin will receive oral moxifloxacin 400 mg q24h for 7 days (7 doses) and oral lefamulin placebo q12h for 5 days (10 doses).

On Day 1, study personnel will administer the first dose of study drug at the study site to all subjects, as soon as possible after the diagnosis of CABP and completion of all required Day 1 procedures as outlined in Table 1. While subjects are hospitalized, all doses of study drug will be administered by hospital staff or study personnel.

For Outpatients, or in the event a subject is discharged from the hospital during the study drug administration period, an adequate supply of study drug will be dispensed for self-administration at home. Subjects will be provided instructions regarding the dosing schedule. Subjects may self-administer oral study drug at home with the following exception: Study personnel will advise subjects who are Outpatients that they must return to the study site to assess CABP signs and symptoms at  $96 \pm 24$  hours after the first dose of study drug (see Section 6.11). Study personnel will inform Outpatients as to the timing of

this required study site visit. Subjects will be advised not to take their first dose of study drug at home that day, rather to bring their blister packs (used and unused) to the study site where they will take their dose while supervised, so that specific assessments can be performed both prior to and after taking the dose (see Sections 6.4 [ECGs] and 6.14 [PK]).

On Study Day 1, if q12h dosing is not feasible, the 1st and 2nd doses may be administered as close as 8 hours apart, in order to allow 2 doses to be given on Day 1. In this circumstance, the subject's dosing schedule should be adjusted on Day 2 to a regular q12h morning and evening schedule. Subsequently, every effort should be made to maintain a q12h dosing schedule. When this is not possible, it is acceptable to administer doses within 4 hours of the scheduled dosing time (i.e., a minimum of 8 hours between doses).

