#### 5.7 Adherence

If subjects are Inpatient, hospital staff or study personnel will administer all doses of study drug and will record the date and time of dosing. In addition, for Outpatients, any doses administered under supervision of study personnel in conjunction with assessments/procedures (e.g., PK sampling, ECGs), study personnel will also record the date and time of those doses.

Outpatient subjects will be instructed to bring all used and unused blister packs to each study visit so that drug accountability can be reviewed by study personnel. Study personnel will collect all blister packs (empty or containing unused study drug) at the EOT visit (see Section 8.3.3). The total number of pills dispensed on Day 1 and returned at the EOT visit will be recorded in the eCRF.

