## 6.1 Inpatient and Outpatient Assessments

As shown in the Schedule of Assessments and Procedures (see Table 1), the timing of assessments and procedures during the Study Drug Administration Period (Days 1-7) may differ between subjects who are Inpatient versus Outpatient.

Hospitalization is not a requirement for this study (i.e., subjects do not need to be admitted to the hospital to participate and those who are admitted may be discharged at any time at the discretion of the investigator).

While Inpatient, all assessments and procedures (including daily study drug administration) will be conducted at the study site/hospital in accordance with the schedule shown in Table 1 (Screening/Baseline through LFU). While Outpatient, the study site must contact the subjects by telephone daily to assess CABP signs and symptoms, assess for the presence of AEs, and determine changes in concomitant medications (see Sections 6.11, 7, and 6.8.2).

All subjects, including Outpatients, must be evaluated by at the investigational site by study personnel at the following time points/visits: Screening/Baseline; Day 1;  $96 \pm 24$  hours after the first dose of study drug; EOT; TOC; and LFU (see Table 1).

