# 6.14 Sample Collection for Pharmacokinetic Analysis

Blood samples for PK analysis of lefamulin and its main metabolite, BC-8041, will be collected in association with the first dose of study drug on Day 1 and Day 4 (see Table 5).

If PK sampling for Inpatients on Day 4 is not feasible, it can be done relative to the first dose on Day 5. For Outpatients, PK sampling will be done during the  $96 \pm 24$  hours post  $1^{st}$  dose visit. Subjects will be instructed to not take their first dose of study drug at home that day, rather to bring all blister packs (used and unused) to the study site. Following collection of the pre-dose blood sample, subjects will take their dose of study drug under supervision of study personnel, and subsequent PK blood samples will be collected.

Table 5. Sample Collection Time Points for the Determination of Lefamulin Plasma Concentrations following Oral Administration

PK Sample Time Point	Day 1 and Day 4 or 96 ± 24 hours post 1 st dose a,b
Within 1 h prior to the first dose of study drug	X
1-2 h after the first dose of study drug	X
3-4 h after the first dose of study drug	X
8-9 h after the first dose of study drug c	X

- a: Day 1 [all subjects] and Day 4 [Inpatients] or 96  $\pm$  24 hours post first dose [Outpatients]
- b: If Day 4 PK sampling for Inpatients is not feasible, it can be done relative to the morning dose on Day 5.
- c: The 8-9 h sample is required for inpatients. The 8-9 h sample is optional for outpatients; however, it should be obtained if logistically feasible.

NOTE: It is essential to record the exact time of dosing on those days when PK samples are obtained (see Section 5.7 – Adherence). Documentation of the exact blood sampling time points for population PK analysis is also essential.

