#### 6.14.1 Sample Collection Methodology

Blood samples for PK analysis will be collected into tubes containing K3EDTA, immediately chilled on crushed ice, and then centrifuged to separate plasma. Promptly following centrifugation, plasma specimens (2 aliquots: 1 for bioanalysis and 1 for backup) will be immediately deep frozen and stored at -20 °C or cooler until transported to the central laboratory. The total time period from blood withdrawal to storage of plasma at -20 °C should not exceed 60 minutes

Additional information and instructions for blood sample collection is provided in the Laboratory Manual.

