#### 9.4.4 Pharmacokinetic Analysis Variables

Population PK modeling will be performed to determine the model-predicted plasma concentration time curves of lefamulin for each subject. Calculated PK will enable descriptive statistical analysis of PK variables such as the maximum observed drug concentration ( $C_{max}$ ) and area under the concentration-time curve (AUC) for lefamulin and its main metabolite, BC-8041. Individual AUC values from Day 1 and Day 4 [i.e., 96  $\pm$  24 hours post first dose] (collected pre-dose, 1-2 h post dose and 3-4 h post dose, and 8-9 h post dose (8-9 h post dose is required for inpatients; optional for outpatients) will be used for the PK/PD analysis. The population PK analysis as well as a PK/PD analysis will be reported separately.

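### Protocol 5.7 and 6.14 do not ask for the time of the home dose that precedes the outpatient 96 ± 24 h pre-dose PK sample

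*Protocol*

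**What the plan says.** Protocol 6.14 sets the timing standard for the PK samples: "It is essential to record the exact time of dosing on those days when PK samples are obtained". It refers to 5.7 for how this is done and also calls exact sampling times essential for the population PK analysis.

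Protocol 5.7 treats the two settings differently. For inpatients, staff give every dose and record its date and time. For outpatients, the requirement is limited to doses supervised in connection with a study procedure ("e.g., PK sampling, ECGs), study personnel will also record the date and time of those doses"). Home doses are covered by blister-pack review and a pill count, dispensed on Day 1 and returned at EOT.

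Under Protocol 6.1, staff are told to "contact the subjects by telephone daily to assess CABP signs and symptoms, assess for the presence of AEs, and determine changes in concomitant medications". Dose times are not on that list.

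Protocol 5.4, 6.1.1 and 6.14 instruct outpatients not to take the first dose at home on the day of the 96 ± 24 h visit. The pre-dose sample is drawn within 1 h before the supervised dose. On dose spacing, 5.4 says that when q12h cannot be kept, "it is acceptable to administer doses within 4 hours of the scheduled dosing time (i.e., a minimum of 8 hours between doses".

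Table 5 of Protocol 6.14 schedules an 8-9 h sample on both PK days, required for inpatients. For the rest, "The 8-9 h sample is optional for outpatients; however, it should be obtained if logistically feasible". Protocol 9.4.4 sends the individual AUC values from these days to the PK/PD analysis.

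**The concern.** A pre-dose concentration can be interpreted only with the time since the previous dose. The protocol holds sites to exact times, yet its rules stop short of the dose that determines this sample. It was taken at home, unsupervised, and normally on a day with no PK sampling.

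The sample carries weight in outpatients. If the 8-9 h draw is not taken on either PK day, the remaining post-dose samples lie within 4 h of dosing. The pre-dose sample at the visit is then that subject's only observation more than 4 h after a lefamulin dose.

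A second situation makes the home dose matter more. Lefamulin ends after ten tablets ("Subjects randomized to lefamulin will receive oral lefamulin 600 mg q12h for 5 days (10 doses"), but the visit window runs beyond the nominal time of the tenth. At a visit after the tenth tablet, no lefamulin is left to take on site, so every PK sample there is timed from a home dose.

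At stake is the dosing history that enters the population PK model, and through it the individual exposures used for PK/PD.

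**Working it through.** The plan states no figure on this point, so there is none to reproduce. The check sets the rules side by side and then illustrates the possible size.

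**Which rule covers the home dose before the visit?**

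| Place | What is timed | Covers that dose? |
|---|---|---|
| Protocol 5.7, inpatients | all doses | No: subject is an outpatient |
| Protocol 5.7, outpatients | supervised doses | No: taken at home |
| Protocol 5.7, pill count | number of pills, no time | No |
| Protocol 6.14 note | doses on PK days | No: normally the day before |
| Protocol 6.1 telephone call | symptoms, AEs, concomitant medications | No |
| Protocol Table 1, footnotes c, x and y | visit procedures, dosing schedule, PK sampling | Not requested |
| SAP 8.4.3, 8.6 and Appendix A | compliance, concentration summary, schedule | Not requested |

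**Gap between last tablet and pre-dose sample**

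Inputs: q12h dosing and the 4 h tolerance (Protocol 5.4). The sample is taken as drawn at the time of the visit dose; it may be up to 1 h earlier.

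- One dose shifted by 4 h: 12 − 4 = 8 h to 12 + 4 = 16 h.
- Extreme case, adjacent doses shifted 4 h in opposite directions: 12 + 4 + 4 = 20 h.

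**Effect on one observed concentration**

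Input: mean IV half-life h of 8.6 to 11.8 h (Protocol 1.5.1). Assumption: log-linear decline, so the concentration is proportional to 2^(−t/h), and the IV value applies to the oral tablet.

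| Comparison | Formula | h = 8.6 | h = 11.8 |
|---|---|---|---|
| 8 h vs 16 h | 2^(8/h) | 1.91-fold | 1.60-fold |
| 8 h vs 20 h (extreme) | 2^(12/h) | 2.63-fold | 2.02-fold |
| true 8 h, 12 h assumed | 2^(4/h) − 1 | +38% | +26% |
| true 16 h, 12 h assumed | 2^(−4/h) − 1 | −28% | −21% |

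**Visit after the last lefamulin tablet**

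- Ten tablets q12h from 0 h: the last falls at 9 × 12 = 108 h.
- Visit window: 96 − 24 = 72 h to 96 + 24 = 120 h.
- The last 120 − 108 = 12 h of the window therefore follow the nominal tenth tablet.

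The safety-laboratory table in SAP Appendix D accepts Day 4, 5 or 6 as this visit, so late visits are foreseen. The documents give neither the number of outpatients nor the share of visits after 108 h.

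**The case against.** The strongest reply is that silence in two protocol sections does not show that the time goes uncollected. The eCRF, the Study Procedure Manual, the Laboratory Manual and the separate population PK analysis plan are not in the documents. Protocol 6.14.1 delegates further detail: "Additional information and instructions for blood sample collection is provided in the Laboratory Manual". The SAP also needs last-dose dates for its EOT and TOC windows, treatment duration and compliance, so some dosing data beyond 5.7 must be collected. This stands as a reason for caution. It does not supply a clock time for the dose in question, and 6.14 sends sites to 5.7, which omits it.

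The opening of Protocol 6 asks for actual procedure times where appropriate, and study drug administration is a row in the schedule. That sentence does not name home doses, and the specific outpatient rule in 5.7 is the better guide to what a site would do.

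Several limits on size are fair:

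- The 4 h tolerance applies only when q12h is not possible, so 8 to 16 h is a permitted range rather than an expected error. The 20 h case is extreme.
- The half-life is an IV value.
- Cmax, Cmin and AUC come from a population model that also uses the timed Day 1 and post-dose samples.
- The concentration summary in SAP 8.6 is by nominal time and does not use the previous dose time.
- A Day 6 visit does not by itself mean that no tablet remains. After a late first dose, the tenth tablet can fall on Day 6 and be taken at the visit. What counts is the hour.
- A Day 1 sample at 8-9 h, where obtained, follows a site-administered dose, which narrows the case in which the visit pre-dose sample is the only late one.

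**Conclusion.** The concern holds as a minor data-capture gap. Followed as written, Protocol 5.7 and 6.14 leave the dose before the outpatient pre-dose sample without a recorded time. They do the same for the dose behind every sample at a visit after the tenth tablet. A time not asked for at the visit is hard to recover later.

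For one observed concentration, the permitted 8 to 16 h gap corresponds to a 1.6- to 1.9-fold difference. Assuming 12 h would miss a true 8 h value by 26 to 38% and a true 16 h value by 21 to 28% in the other direction. These figures rest on log-linear decline at the IV half-life. They do not carry over to AUC or to PK/PD, where the effect is unknown. Pharmacokinetics is an additional objective (Protocol 2.3); no efficacy endpoint, analysis set or non-inferiority conclusion changes.

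Confidence is medium, because documents not available here may already capture the time.

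**What to change.** In Protocol 5.7 and 6.14, have study personnel ask at the 96 ± 24 h visit for the date and time of the last lefamulin-or-placebo tablet taken before the pre-dose PK sample, and record it in the eCRF. If it is already collected, state where. Use the recorded time in the population PK analysis.

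The cost is one eCRF field and one sentence in each section. No extra visit is needed, since the subject is already on site with the blister packs. The drawback is that the time is self-reported; it is still better than an assumed 12 h.

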#### 6.14.1 Sample Collection Methodology

Blood samples for PK analysis will be collected into tubes containing K3EDTA, immediately chilled on crushed ice, and then centrifuged to separate plasma. Promptly following centrifugation, plasma specimens (2 aliquots: 1 for bioanalysis and 1 for backup) will be immediately deep frozen and stored at -20 °C or cooler until transported to the central laboratory. The total time period from blood withdrawal to storage of plasma at -20 °C should not exceed 60 minutes

Additional information and instructions for blood sample collection is provided in the Laboratory Manual.

## 6.14.2 Assay Methodology

Plasma samples from subjects who received lefamulin will be analyzed for the concentration of lefamulin and its main metabolite, BC-8041, using a validated liquid chromatographytandem mass spectrometry method at the bioanalytical laboratory A&M GmbH (Bergheim, Germany). Samples from subjects who did not receive lefamulin (i.e., received the comparator) will not be analyzed. Scientists at the bioanalytical laboratory will be unblinded before bioanalysis.

## **6.15 Microbiological Assessment**

The following microbiological assessments will be performed at the time points described in Table 1. Details regarding storage of samples and shipment to the central laboratory can be found in the Laboratory Manual.

## 6.15.1 Sputum Samples

- A sputum sample will be taken at Screening for Gram's staining, culture and susceptibility testing at the local/regional laboratory. If a subject is unable to produce an adequate (> 25 polymorphonuclear (PMN) cells AND < 10 squamous epithelial cells per LPF) sputum sample at Screening, a repeat specimen should be obtained, if possible, within 24 hours after the first dose of study drug. Gram's stain and culture results from the local/regional laboratory will be recorded in the eCRF.

- If possible, subjects who are discontinued from study drug due to clinical failure should have repeat cultures collected for microbiologic culture prior to switching to alternate appropriate therapy.
- Sputum samples will only be taken at subsequent visits when clinically indicated.
- All organisms isolated from sputum samples which are not considered contaminants will be sent to the central laboratory for confirmatory identification and susceptibility testing. The following organisms, if isolated, will always be sent to the central laboratory for confirmatory identification and susceptibility testing: *S. pneumoniae*, *S. aureus*, *S. pyogenes*, *Haemophilus* spp., *M. catarrhalis*, *L. pneumophila*, *C. pneumoniae*, and *M. pneumoniae*. Further details regarding organisms which should be sent to the central microbiology laboratory, including a list of organisms which if isolated will be classified as contaminants, can be found in the Laboratory Manual.
- Gram's stain slides will be sent to the central laboratory for a confirmatory reading. The stained slide read by the local/regional laboratory as well as an unstained slide will be sent to the central laboratory.
- A portion of each Screening sputum sample taken will be frozen until shipment to the central laboratory. Frozen samples will be analyzed by the central microbiological laboratory using real-time quantitative PCR for common CABP pathogens. Additionally, for subjects who have a positive urinary antigen test for *Legionella* spp. the frozen sputum will be utilized for *L. pneumophila* isolation and susceptibility testing.

## 6.15.2 Bronchoalveolar Lavage Samples (BAL)

A BAL sample is not required per the protocol and will be collected only if clinically indicated per the Investigator, and sent to the local/regional laboratory for Gram's staining, culture and susceptibility testing. However, if the subject undergoes a repeat bronchoscopy as clinically warranted per the investigator, a repeat BAL sample should be sent for Gram's staining and culture. All organisms isolated from BAL samples, which are not considered contaminants, will be sent to the central laboratory for confirmatory identification and

susceptibility testing. Culture results from the local/regional laboratory will be recorded in the eCRF.

## 6.15.3 Pleural Fluid Samples

A pleural fluid sample is not required per the protocol, and will be collected only if clinically indicated per the Investigator and sent to the local/regional laboratory for Gram's staining, culture and susceptibility testing. However, if the subject undergoes a repeat thoracentesis as clinically warranted per the Investigator, a repeat pleural fluid sample should be sent for Gram's staining and culture. If possible, pleural fluid samples should be incubated in blood culture bottles for optimal pathogen recovery. All organisms isolated from pleural fluid samples which are not considered contaminants will be sent to the central laboratory for confirmatory identification and susceptibility testing. Culture results from the local/regional laboratory will be recorded in the eCRF.

#### 6.15.4 Blood Cultures

Two sets of blood cultures via venipuncture will be obtained at Screening and sent to the local/regional laboratory. Repeat blood samples for culture should be taken as clinically indicated during the study. Blood cultures should be repeated after a positive result until sterilization is documented. All organisms isolated from blood cultures which are not considered contaminants will be sent to the central laboratory for confirmatory identification and susceptibility testing. Subjects who have confirmed bacteremia should have blood samples collected for microbiologic culture prior to switch to alternate appropriate therapy. Subjects who have confirmed *S. aureus* bacteremia must be withdrawn from the study. Culture results from the local/regional laboratory will be recorded in the eCRF.

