- b: Day 1 is the first day of study drug administration; subsequent study days are consecutive calendar days. Assessments/ procedures on Day 1 should be performed prior to first dose.
- c: INPATIENTS will be assessed daily while hospitalized; thus, data required for ECR Assessment (96 ± 24 hours after the first dose of study drug) will be collected.

  OUTPATIENTS must have a visit at the study site that is 96 ± 24 hours after the first dose of study drug to assess CABP signs and symptoms for calculation of ECR. Study personnel will inform subjects as to the timing of this visit during the course of daily telephone contact. In addition to the assessment of CABP signs/symptoms, subjects will also have the following procedures/assessments performed at that study site visit: ECGs, physical examination, AE monitoring, review of concomitant medications, vital signs, oxygen saturation, and blood sampling for PK analysis and safety laboratory evaluations. Importantly, study personnel will advise OUTPATIENTS not to take their first dose of study drug at home that day, rather to bring their blister packs (used and unused) to the study site where they will take their dose while supervised; thus, specific assessments can be performed both prior to and after taking the dose (i.e., ECGs and PK). See Footnotes i, k, l, m, o, p, and y below for details.
- d: Perform End of Treatment (EOT) assessments at the study site within 1 day (up to 2 days permitted) after the last dose of study drug or at the time of premature discontinuation of study drug or early withdrawal from study. EOT assessments resulting from premature discontinuation of study drug should be done in place of the regular study visit on Days 1 to 7.
- e: Perform Test of Cure (TOC) assessments at the study site 5–10 days after the last dose of study drug. All subjects will have a TOC Visit irrespective of early clinical failure or receipt of an alternative antibiotic.
- f: Perform Late Follow Up (LFU) assessments at the study site on Day 30 ± 3 days. All subjects will have a LFU Visit irrespective of early clinical failure or receipt of an alternative antibiotic.
- g: Obtain informed consent before initiating any study-specific assessments or procedures.
- h: Assessment or procedure may occur at either Screening OR prior to the first dose of study drug on Day 1 once eligibility has been determined.

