- t: Collect blood samples (2 sets via peripheral venipuncture) for microbiologic culture and susceptibility testing at the local/regional lab at Baseline and as clinically indicated during the study. Repeat blood cultures after a positive result until sterilization is documented. If possible, subjects who are discontinued from study drug due to confirmed MRSA or MSSA bacteremia should have blood samples collected for microbiologic culture prior to switching to alternate appropriate therapy. All organisms isolated from blood cultures which are not considered contaminants will be sent to the central laboratory for confirmatory identification and susceptibility testing.
- u: All lower respiratory tract and expectorated sputum samples should be sent to the local/regional laboratory for Gram's stain, culture and susceptibility testing. A sputum sample will be taken at Screening for Gram's staining, culture and susceptibility testing at the local/regional laboratory. If a subject is unable to produce an adequate (> 25 polymorphonuclear [PMN] cells AND < 10 squamous epithelial cells per LPF) sputum sample at Screening, a specimen should be obtained, if possible, within 24 hours after the first dose of study drug. Gram's stain and culture results from the local/regional laboratory will be recorded in the eCRF. Slides (stained and unstained) will also be sent to the central laboratory for a confirmatory reading of the Gram's stain. If possible, subjects who are discontinued from study drug due to clinical failure should have repeat cultures collected for microbiologic culture prior to switching to alternate appropriate therapy. All organisms isolated from sputum samples, which are not considered contaminants, will be sent to the central laboratory for confirmatory identification and susceptibility testing. In addition, a portion of all Baseline sputum samples must be frozen until sent to the central laboratory for quantitative PCR. Subjects with a urinary antigen positive for Legionella spp. will also have a portion of their sputum sample sent frozen to the central laboratory for isolation of L. pneumophila.

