#### 6.18.2 Discontinuation from Study

A subject may be discontinued prematurely from the study for the following reasons:

- Withdrawal by subject [specify reason in the eCRF]
- Lost to follow-up
- Death
- Physician decision (i.e., assessment that it is not in the subject's best interest to continue, or other reason) [specify reason in the eCRF]
- Sponsor decision [specify reason in the eCRF]

Every attempt will be made to contact subjects who withdraw from the study in order to determine their vital status (alive or dead) at Day 28.

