## 6.18.3 Individual Stopping Criteria

Subjects will be withdrawn from the study drug treatment for any of the following reasons:

- The subject demonstrates an average QTcF value > 500 ms (mean of 3 ECG's at any time point) as assessed locally by the Investigator. Such subjects should be observed until the ECG normalizes with repeat ECG's taken at the discretion of the investigator.
- The subject demonstrates an average QTcF value > 480 ms with a concurrent increase in average QTcF value of > 60 ms (mean of 3 post-dose ECGs compared to mean pre-dose ECGs taken on that day) as assessed locally by the Investigator.
- The subject has confirmed *S. aureus* bacteremia.

If a subject is prematurely withdrawn from study treatment, the Investigator should make every effort to retain the subject in the study and to perform all procedures scheduled for the EOT, TOC, and LFU visits. Any subject withdrawn from treatment due to an AE, SAE, or clinically significant abnormal laboratory test value will be evaluated by the Investigator, or a

monitoring physician, and will be treated and/or followed up until the symptoms or values have either resolved or are assessed as stable by the Investigator.

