- d: Perform End of Treatment (EOT) assessments at the study site within 1 day (up to 2 days permitted) after the last dose of study drug or at the time of premature discontinuation of study drug or early withdrawal from study. EOT assessments resulting from premature discontinuation of study drug should be done in place of the regular study visit on Days 1 to 7.
- e: Perform Test of Cure (TOC) assessments at the study site 5–10 days after the last dose of study drug. All subjects will have a TOC Visit irrespective of early clinical failure or receipt of an alternative antibiotic.
- f: Perform Late Follow Up (LFU) assessments at the study site on Day 30 ± 3 days. All subjects will have a LFU Visit irrespective of early clinical failure or receipt of an alternative antibiotic.
- g: Obtain informed consent before initiating any study-specific assessments or procedures.
- h: Assessment or procedure may occur at either Screening OR prior to the first dose of study drug on Day 1 once eligibility has been determined.
- i: All subjects will have vital signs and O2 saturation evaluated at Screening/Baseline and Day 1. If screening/baseline and Day 1 occur on the same calendar day, vital signs and O2 saturation do not need to be repeated. All subjects will also have assessments at EOT and TOC; at LFU, vital signs should be performed if medically indicated. If EOT and the last day of study drug are the same day, vital signs do not need to be repeated, they may be recorded once on that day (i.e., as part of the EOT assessment). Record the vital signs associated with the highest temperature after the first dose of study drug.  
**INPATIENTS:** Vital signs, O2 saturation, and supplemental O2 usage will be measured daily. If multiple vital signs are taken on a study day, the highest temperature and the vital signs associated with that high temperature will be recorded.  
**OUTPATIENTS:** In addition to the above time points, vital signs, O2 saturation and, if applicable, supplemental O2 usage will be measured at the study visit scheduled 96 ± 24 hours after the first dose of study drug.

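### Confirmed S. aureus bacteremia means leaving the study in three places in the protocol, but only stopping study drug, with follow-up continuing, in Section 6.18.3 and Table 1

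*Protocol*

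**What the plan says.** **Withdrawal from the study.** Three places in the current protocol carry the same instruction: the Synopsis (Study Design), Section 3 and Section 6.15.4 (Blood Cultures). Subjects with confirmed S. aureus "bacteremia must be withdrawn from the study".

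**Stopping study drug, with follow-up.** Section 6.18.3 (Individual Stopping Criteria) opens with "Subjects will be withdrawn from the study drug treatment for any of the following reasons", and confirmed S. aureus bacteremia is one of the listed reasons. It continues: "If a subject is prematurely withdrawn from study treatment, the Investigator should make every effort to retain the subject in the study", and asks for all EOT, TOC and LFU procedures.

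Table 1 is written the same way. Footnote t, repeated in SAP Appendix A, refers to "subjects who are discontinued from study drug due to confirmed MRSA or MSSA bacteremia". Footnote e states: "All subjects will have a TOC Visit irrespective of early clinical failure or receipt of an alternative antibiotic". Footnote f makes the same provision for LFU: "All subjects will have a LFU Visit irrespective of early clinical failure or receipt of an alternative antibiotic".

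**Reasons for leaving the study.** Section 6.18.2 begins "A subject may be discontinued prematurely from the study for the following reasons" and gives a list that does not name S. aureus bacteremia. For subjects who leave, it provides a contact to establish vital status at Day 28.

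**The concern.** The two instructions cannot both be followed. The protocol treats stopping treatment (Section 6.18.1) and leaving the study (Section 6.18.2) as separate events with separate follow-up, so this is not a loose use of synonyms. The introduction to Section 6.18 adds that a withdrawn subject may not come back, so a site that picks the wrong reading cannot correct it.

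The withdrawal wording is also the firmer of the two. It is mandatory, it appears three times, and one of those is the section a site would open on receiving a positive blood culture. The retention rule asks only for every effort. Section 6.15.4 sits awkwardly even with itself, since it also wants cultures repeated until the blood is sterile.

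At stake is post-treatment safety follow-up in a small, high-risk group: bacteremic subjects who stop study drug early and change therapy. If sites read the rule differently, the same clinical event will also be coded differently in the disposition table.

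**Working it through.** The plan states no figure on this point, so the check is a comparison of what each reading keeps and loses.

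| Item | Withdrawn from the study | Study drug stopped, subject retained |
|---|---|---|
| EOT assessments | Kept: Table 1 footnote d requires them "at the time of premature discontinuation of study drug or early withdrawal from study" | Kept |
| TOC visit (vital signs, examination, safety laboratory tests, SF-12, AE review) | Lost | Kept |
| LFU visit, including convalescent serology | Lost | Kept |
| New non-serious AEs between EOT and TOC | Lost: collection runs through TOC (Section 7) | Kept |
| SAEs to 30 days after last treatment (Section 7.3) | Still due, without the scheduled visits | Kept |
| Day 28 vital status (Sections 6.18.2, 6.18.4) | Still sought by contact | Normally settled by the LFU visit |
| SAP 8.1 disposition | Drug discontinuation and study withdrawal | Drug discontinuation only |

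**AE collection lost per subject.** The inputs are the Table 1 windows: EOT 0 to 2 days and TOC 5 to 10 days after the last dose.
- Shortest gap: 5 − 2 = 3 days.
- Longest gap: 10 − 0 = 10 days.

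**LFU visit lost.** Day 30 ± 3, that is Day 27 to Day 33.

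**Disposition.** With 369 subjects planned per arm (Protocol 9.2), one subject coded as a study withdrawal adds 1/369 = 0.0027, or 0.27 percentage points, to that arm. SAP 8.1 compares the percentage withdrawn from the study and the percentage discontinued from study drug between arms with Fisher's exact test.

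**Safety tables.** SAP 8.7.2 summarizes laboratory change from baseline at Day 4, EOT and TOC. A withdrawn subject contributes nothing at TOC.

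**Mortality.** SAP 6.2.4 counts subjects of unknown Day 28 status as deceased, and SAP 8.5.3.5 shows those lost to follow-up separately. Because vital status is still sought after withdrawal, the effect is weaker ascertainment rather than an automatic count as a death.

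**Efficacy.** A subject who needs additional antibiotic treatment for the current pneumonia is an IACR Failure (Sections 6.8.2 and 6.12.1). Failure at EOT carries forward to TOC, so the TOC outcome is normally not lost.

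**The case against.** The strongest reply is that the operative rule is already in the protocol. Section 6.18.3 is the dedicated stopping section, names this event and limits the action to study drug. The visit schedule agrees with it. The three conflicting places are one sentence repeated, two of them in summaries. Harm requires a site to follow that sentence and overlook Section 6.18.3 and Table 1.

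It can also be said that little is lost. After an IACR Failure, symptoms and IACR are not collected at TOC or LFU anyway. LFU laboratory samples are taken only after an abnormal TOC result, and LFU vital signs only if medically indicated. The missing AE interval falls after study drug has stopped: with the reported IV half-life of up to 11.8 h, five half-lives are 5 × 11.8 = 59 h, about 2.5 days. Suspected or confirmed MRSA pneumonia is excluded at entry, which shrinks the group further. A shift of 0.27 points in a disposition percentage changes no efficacy or safety conclusion.

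Most of this stands as a limit on size. The efficacy content of the later visits would usually be absent in any case, and the numbers are likely to be small. It does not remove the conflict. Section 6.15.4 is not a summary, its instruction is mandatory, and a site that obeys it drops TOC safety laboratory tests, vital signs and examination, AE review and LFU serology that the protocol elsewhere requires. That Section 6.18.3 appears to be the intended rule is a reason to correct the other three places.

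**Conclusion.** The point holds. The current text gives two incompatible instructions for the same event, and following the mandatory one loses scheduled safety follow-up.

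The size is modest: per affected subject, the TOC visit, the LFU visit and 3 to 10 days of new non-serious AE collection, plus 0.27 percentage points on that arm's study-withdrawal percentage. These figures assume that EOT and TOC would have fallen within their windows and that each arm reaches 369 subjects. The documents give no expected number of cases, so no total can be stated. No bias is claimed in ECR or in IACR at TOC in the mITT or CE-TOC sets, and for SAEs and mortality the effect is limited to weaker ascertainment.

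**What to change.** Keep the rule in Section 6.18.3. In the Synopsis, Section 3 and Section 6.15.4, reword the sentence so that subjects with confirmed S. aureus bacteremia must be withdrawn from study drug treatment, with follow-up as set out in Section 6.18.3.

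The cost is one sentence changed in three places in the protocol. Section 6.18.3, the Table 1 footnotes and the SAP need no change, there are no new procedures, and these subjects still stop study drug exactly as now.
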